#### Cohort 2:

Fifteen patients undergoing comprehensive orthodontic treatment with fixed appliances at the University of Minnesota, who are willing to participate, will have their mandibular incisor brackets removed and EXD-952 brackets placed instead. Other mandibular brackets will remain in place. A rectangular Stainless Steel archwire (0.017x0.025" or 0.019x0.025") will be used as a working mandibular archwire. The perceived ability of the bracket to hold the archwire, ease of handling, and ease of opening/closing the door will be assessed using a custom-designed survey. After the first adjustment visit after placement of EXD-952 brackets (expected 6-8 weeks later) the bracket's ability to control inclination of teeth, clinicians' satisfaction with the bracket, and patient comfort in comparison with other brackets will be assessed using custom-designed surveys. There will be photodocumentation at the bonding appointment and at the adjustment visit. Any bracket failures (e.g. decementation, failure of door etc.) and adverse events will be documented. The initial evaluation for each patient will last for at least one appointment interval (6-8 weeks).

After the evaluation period, EXD-952 Ceramic Self-ligating brackets will remain in place until the orthodontic treatment is completed.

If EXD-952 brackets fail in the course of the study they will be initially replaced with EXD-952 brackets. Should the same EXD-952 brackets fail for a second time in the same patient, all EXD-952 brackets will be removed and replaced with conventional brackets. 3M will cover the cost for replacing failed brackets.

#### 4.7 STUDY TERMINATION/SUBJECT DISCONTINUATION OR WITHDRAWAL

Conditions that may warrant termination of the study include but are not limited to the following:

- The discovery of an unexpected, serious, or unreasonable risk to study subjects;
- Insufficient adherence to protocol requirements;
- Submission of knowingly false information from the Investigator to 3M Oral Care;
- Termination/withdrawal of IRB approval;

- A decision on the part of 3M Oral Care to suspend or discontinue evaluation of the investigational product. In this case, patients will finish their treatments with the study brackets in place but brackets will no longer be evaluated.

#### 4.7.1 Subject Discontinuation

- Subjects may withdraw from the study at any time. EXD-952 brackets will remain in place unless the patients requests the brackets to be removed.
- The Investigators may exclude individual subjects from the study at any time in the event of illness, adverse events, lack of compliance, treatment failure, protocol deviations, administrative reasons, or other reasons that would render the subject unsuitable for the purposes of this study.
- A subject will be removed from the study if two or more ( $\geq 50\%$ ) study brackets have been classified as failed. In that case, all EXD-952 brackets placed in the subject will be removed and replaced with conventional brackets
- The trial will be terminated for safety reasons if the cumulative failure rate of study brackets reaches or exceeds 50%.

In case of study withdrawal and subsequent drop-out, there will be no subject replacement. Date and reason for withdrawal will be recorded. The data collected on the subject to the point of withdrawal remains part of the study database unless the subject expresses that the data be erased. There will be no additional follow-up data collected after subject withdrawal.

In case of an adverse event, the specific event will be recorded on the Adverse Event Report Form and communicated to the IRB. The subject will be followed until the event is resolved.

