| Description of Study Procedure: | 
A cohort of 15 patients starting orthodontic treatment with fixed appliances will receive EXD-952 Ceramic Self-ligating bracket on all mandibular incisors and a different type of brackets on the remaining mandibular teeth. Tooth movement will be initiated using 0.014" or 0.016" Nickel-Titanium archwires.
 
A second cohort of 15 patients will receive EXD-952 Ceramic Self-ligating bracket on all mandibular incisors in a later phase of their ongoing orthodontic treatment. The mandibular incisor brackets will be removed and EXD-952 Ceramic Self-ligating brackets placed instead. Other mandibular brackets will remain in place. Tooth movement will be performed using 0.019x0.025" Stainless Steel archwires.
 
In both cohorts bracket door stability, the ability of the door to hold the archwire in the bracket slot, the bracket's ability to rotate teeth, clinicians' satisfaction with the bracket, and patient comfort in comparison with other brackets will be assessed.
 
The evaluation for each patient will last for at least until one archwire change (cohort 1) or one appointment interval (6-8 weeks, cohort 2).
 
After the evaluation period, EXD-952 Ceramic Self-ligating brackets will remain in place until the orthodontic treatment is completed.
 |
| Reports:                        | 
Reports will be prepared after the initial evaluation period (Initial Report), at the end of each year over the course of the study (Annual Reports), and after all patients have completed treatment (Final Report).
   |

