#### 4.5 REPORTING PERIODS

The PI will provide the Sponsor with the following written reports:

Initial report: This report will be provided within 60 days after all study subjects in cohort 1 have completed one archwire change and all subjects in cohort 2 had at least one adjustment visit after placement of the investigational brackets. This report will include data related to the primary outcome measures.

Annual progress reports: Progress reports will be provided annually and will include data on bracket failure and adverse events until all study subjects have completed orthodontic treatment.

Final report: A final report will be provided after all study subjects have completed orthodontic treatment.

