#### 7.4 TIME PERIOD FOR PRINCIPAL INVESTIGATOR TO REPORT ADVERSE EVENTS

The PI shall:

- a) record every adverse event and observed device deficiency, together with an assessment of the event and report it to the local IRB and to 3M Oral Care as soon as possible and without undue delay;
- b) report all serious adverse events and all adverse events and device deficiencies that could have led to a serious adverse device effect to the local IRB and to 3M Oral Care within 24 hours or sooner if possible after becoming aware of the situation; this information shall be promptly followed by detailed written reports as necessary so that 3M Oral Care can evaluate the event and report to the proper regulatory authority and/or IRB;
- c) supply the local IRB and 3M Oral Care with any additional requested information related to the safety reporting of a particular event.

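### Read as failed over placed, the bracket failure rate is capped by removing subjects at two failures, so the 50% trial stop seldom fires at 50% true failure when failures are spread over several visits

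*Combined protocol and SAP*

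**What the plan says.** Each subject carries four study brackets. For cohort 2 the synopsis (section 1) states: "A second cohort of 15 patients will receive EXD-952 Ceramic Self-ligating bracket on all mandibular incisors"; cohort 1 is bonded on the same teeth.

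Section 4.7.1 then sets two rules next to each other. At subject level, two or more failed brackets, which the text equates with at least 50%, end participation: "In that case, all EXD-952 brackets placed in the subject will be removed and replaced with conventional brackets". At trial level: "The trial will be terminated for safety reasons if the cumulative failure rate of study brackets reaches or exceeds 50" per cent. The same section does not replace withdrawn subjects, collects nothing after withdrawal, and keeps the data already collected.

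On single failures, section 4.6 says: "If EXD-952 brackets fail in the course of the study they will be initially replaced with EXD-952 brackets". It adds: "Should the same EXD-952 brackets fail for a second time in the same patient, all EXD-952 brackets will be removed".

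Nothing defines the numerator, the denominator, how replacements count, or when the rate is checked. The synopsis plans only to calculate a bracket failure rate, and section 8 offers only descriptive statistics.

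**The concern.** The two rules act on the same count. A removed subject's brackets stay in the denominator, but those that had not failed are taken out and can no longer fail. The subject rule therefore censors the quantity that the trial rule watches.

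This is the only numerical stop for the trial as a whole, and it is worded as mandatory and for safety. An IRB would expect it to act when about half of the brackets fail. On the simple reading it may stay silent well above that level, while the reported rate understates the failure rate of the device.

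The bullet also leaves open what happens to the brackets of subjects still wearing them after a safety stop. Section 4.7 addresses this only for a sponsor decision to discontinue: "In this case, patients will finish their treatments with the study brackets in place but brackets will no longer be evaluated".

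**Working it through.** The plan gives no expected failure rate, failure timing or operating characteristic, so there is no figure to reproduce.

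**Inputs from the documents.** 30 subjects; 4 study brackets each, so 120; removal at 2 or more failures; trial stop at 50%; visits 6-8 weeks apart; study duration 2-3 years.

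**Assumptions.** All 30 subjects are bonded; brackets fail independently with a constant hazard; each has probability q of failing over treatment if left in place; failures are counted at V visits. 18 visits at 7 weeks is 126 weeks, about 2.4 years. The other visit counts are also assumed. Replacements are ignored except in step 1.

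**1. Ceiling.** With failures found singly, each subject adds at most 2 of 4, so the maximum is (30 × 2)/(30 × 4) = 60/120 = 50%, reached at the 30th removal. If the first failure is replaced and the replacement counts as placed, each subject has 5 brackets: 60/150 = 40%.

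**2. Reference with no removal rule.** P(Bin(120, 0.5) ≥ 60) = 53.6%.

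**3. Removal rule, failures found singly, q = 0.5.** P(X ≥ 2) = 1 − 1/16 − 4/16 = 0.6875. P(stop) = 0.6875^30 = 0.000013. Mean counted failures are (4 × 1 + 11 × 2)/16 = 1.625 per subject, an observed rate of 1.625/4 = 40.6%.

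**4. Removal rule, failures found at visits.** The per-visit hazard is h = 1 − (1 − q)^(1/V). A subject with k = 0 or 1 failures gains Bin(4 − k, h) at each visit and leaves when the total reaches 2 or more, so 3 or 4 can be counted if found together. Adding the 30 subjects' distributions by convolution gives P(total ≥ 60):

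| Visits | q = 40% | q = 50% | q = 60% | q = 70% | Even chance at q of about |
|---|---|---|---|---|---|
| 18, both cohorts | <0.001% | 0.1% | 5% | 43% | 71% |
| 18 in cohort 1, 6 in cohort 2 | 0.001% | 0.4% | 14% | 68% | 67% |
| 4, both cohorts | 0.01% | 3% | 45% | 94% | 61% |
| 2, both cohorts | 0.1% | 16% | 82% | 99.8% | 55% |
| 1 (cap never acts) | 1.7% | 54% | 99% | >99.9% | 50% |

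At q = 50% the mean observed rate is 41% with 18 visits, 43% with 4 and 50% with 1. When the stop does fire, a median of 27-28 of the 30 subjects are already off with 18 visits, and 25-26 with 4.

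**5. Quantities that removal does not cap.** At q = 0.5 the expected number of subjects meeting the removal rule is 30 × 0.6875 = 20.6, so 21 of 30 is the matching level. P(Bin(30, P(X ≥ 2)) ≥ 21) is 0.01%, 4%, 53% and 97% at q = 30%, 40%, 50% and 60%, with a median of 21 (18 visits) or 22-24 (4 visits) subjects off at the stop. A Kaplan-Meier bracket failure rate, censored at removal, reaches 50% in 49% of trials at q = 50%, with either 18 or 4 visits.

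**6. Failures clustered within subjects.** With a beta-binomial correlation of 0.2 at q = 0.5, P(X ≥ 2) = 0.629, or 30 × 0.629 = 18.9 subjects. Then 21 of 30 fires 27-28% of the time, Kaplan-Meier 20-25%, and the crude rule 0.02% (18 visits) to 2% (4 visits).

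**The case against.** **The rate is undefined.** A Kaplan-Meier rate would not be capped, so the text does not prove that the stop fails. This stands, and the point is conditional on the crude reading. That reading is still the natural one, since the plan promises only a failure rate and descriptive statistics.

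**A reader might infer that the stop can never be reached.** The documents do not support that. Several failures can be found at one visit, which lifts the rate past 50%. First checks come 6-8 weeks after bonding, so early failures found together are plausible, and no failure timing is given. With a denominator of brackets placed to date, the rule could even fire on the first subject, at 2 of 4.

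**The benchmark is external.** Section 4.7.1 names an observed rate, not the failure probability had brackets stayed in. This is fair, but a safety threshold whose meaning depends on how fast subjects are removed is hard to interpret.

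**Eighteen visits for everyone is too many.** Cohort 2 is bonded late in treatment. This stands: with an assumed 6 visits for cohort 2, the even chance falls from 71% to 67%. The direction is unchanged.

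**Little changes for patients.** This largely stands. All subjects are assumed already bonded, 21-24 rather than 25-28 would be off when the stop fires, and the subject rule still protects the rest. Other oversight also exists. On the initial report, section 4.5 says: "This report will include data related to the primary outcome measures". Annual reports cover bracket failure. Section 7.4 requires the investigator to "record every adverse event and observed device deficiency" and report it promptly; the sponsor reviews deficiencies (7.5) and CRFs (9), and the termination grounds in 4.7 are open-ended. None of this repairs a mandatory trigger, but it limits the harm.

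**The remedy also depends on unknown correlation.** True: step 6 shows it. The matching level shifts, but the subject proportion is still not capped by removal.

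**Conclusion.** The concern holds on the failed-over-placed reading and when failures are spread over several visits. At 50% true bracket failure the stop then fires in about 0.1% to 3% of trials (18 to 4 visits), against 54% without the removal rule. The shortfall is smaller with 2 visits (16%) and absent with one. These figures rest on full enrolment, independent brackets, a constant hazard and assumed visit counts; no figure is claimed for the accrual phase.

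A reader might go further and conclude that the trial has no working safety stop or that patients are left unprotected. The documents do not support this: each subject is protected by the two-failure rule, and the sponsor and IRB can end the trial on other grounds. This is a modest defect that should be fixed because it is an interaction between two stated rules and is cheap to correct.

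**What to change.** Amend the trial-level bullet in section 4.7.1 so that the stop uses a quantity that subject removal does not cap. The simplest is the proportion of bonded subjects who have met the two-failure removal rule, recalculated at each removal. To keep the present 50% bracket tolerance, set it at about 21 of 30 if brackets are independent, and somewhat lower (about 63% of subjects, or 19 of 30) if the within-subject correlation is 0.2. A Kaplan-Meier bracket failure rate, censored at subject removal, is an alternative. A stricter level, such as 15 of 30, is a new tolerance for the sponsor and IRB to choose, not a correction.

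The bullet should also state the minimum number of bonded subjects before the rule applies, how replacements and repeat failures at one position count, and whether remaining wearers keep their brackets after a safety stop.

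The cost is one protocol amendment, with no extra patients or procedures. The downside is small: at 21 of 30 there is about a 4% chance of stopping at 40% true failure, against about 0% now when failures are spread over several visits.

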### 4.8 DROP-OUT ESTIMATION

Considering the short study duration, the estimated drop-out rate is expected to be low. Therefore, there will be no over-recruitment of subjects.

### 4.9 PROTOCOL MODIFICATIONS

#### 4.9.1 Protocol Amendments

The party initiating an amendment must confirm it clearly in writing using the Amendment/Administrative Revision form. It must be signed and dated by 3M Oral Care and, in the case of a significant amendment, the Principal Investigators (PIs). A significant amendment means one that affects the safety, rights or welfare of subjects, the scope of the investigation, or the scientific quality of the study.

3M Oral Care will submit significant protocol amendments to the PIs for submission to the IRB. 3M Oral Care will also notify the PIs when a protocol amendment may be implemented.

#### 4.9.2 Protocol Deviations

A deviation is a departure from the protocol that will likely affect the safety, rights or welfare of subjects, the scope of the investigation or the scientific quality of the study.

A protocol deviation is only for an individual subject. Protocol deviations are documented on the appropriate CRF and on the Protocol Deviation Form.

Deviations that potentially affect (1) subject safety, rights or welfare, (2) data integrity or (3) compromise the statistical analysis of the study require immediate communication to 3M Oral Care. The PI will contact and submit a completed Protocol Deviation Form to the 3M Oral Care study monitor within 24 hours of identifying the occurrence.

## 5. INCLUSION / EXCLUSION CRITERIA

### Inclusion Criteria:

- Mandibular permanent dentition including incisors, canines, premolars, and first molars (includes subjects treated with the extraction of premolars)
- Mandibular incisors with sound, non-carious buccal enamel and no pretreatment with chemical agents such as hydrogen peroxide

### Exclusion Criteria:

- Mental/emotional/developmental disability
- Inability to give informed consent
- Cleft lip and/or palate, craniofacial anomaly, or syndrome
- Obvious oral hygiene issues such as excessive plaque accumulation, gingivitis, and/or pre-existing white spot lesions
- Prosthodontic or restored substrate extending on the labial surface of mandibular incisors
- Deep bite
- Known allergies to any study materials

### 5.1 SUBJECT CONSENT

The PI must ensure that written informed consent to participate in the investigation is obtained before including any individual as a subject in the investigation. The PI must provide the prospective subject or their legal representative sufficient opportunity to consider whether or not to participate, and minimize the possibility of coercion or undue influence. The process is designed to 1) give the subject all the information that they need, 2) ensure that the subject understands the information and 3) give the subject a chance to consider study participation. The process should permit the subject to ask questions and exchange information freely.

## 6. PRIMARY OUTCOME MEASURES

- Bracket door stability
- Ability of door to hold the archwire in the bracket slot
- Bracket's ability to rotate teeth
- Clinicians' satisfaction with the bracket
- Patient comfort in comparison with other brackets

## 7. ADVERSE EVENTS

Adverse events will be recorded immediately with attention to the onset, severity, and duration of the event as well as its relationship to the study product using the Adverse Event Reporting Form. In the event that the described research activity results in an injury, treatment will be available, including first

aid, emergency treatment, and follow-up care as needed. Care for such injuries will be billed in the ordinary manner to the patient's insurance company. In the event that the described research activity results in tooth damage such as wear of enamel surfaces of teeth in contact with the bracket, tooth damage upon debonding and/or losing fractured portions of the bracket in the patient's mouth, treatment will be available at the study sponsor's expense. Any treatment in response to the adverse event will be noted and the subject must be followed until resolution.

All adverse reactions will be reported to the local IRB and to 3M Oral Care (in this order) as soon as possible and without undue delay. All serious adverse events will be reported to the local IRB and to 3M Oral Care within 24 hours or sooner if possible after becoming aware of the situation. Subjects removed from study participation at the request of the sponsor or clinical team receive full compensation for their participation.

Any clinically significant abnormal laboratory finding, serious or unanticipated Serious Adverse Event or other medical event which results in the withdrawal of a subject from the study must be followed until resolution with appropriate medical management or as deemed necessary (with the Sponsor's agreement).

#### 7.1 ADVERSE EVENTS AND ADVERSE DEVICE EFFECTS

**Adverse Event (AE)** – Any untoward medical occurrence, unintended disease or injury, or untoward clinical signs (including abnormal laboratory findings) in subjects, users or other persons, whether or not related to the tested medical device.

Note 1: this definition includes events related to the investigational medical device or the comparator.

Note 2: this definition includes events related to the procedures involved.

Note 3: for users or other parties, this definition is restricted to events related to investigational medical devices.

**Adverse Device Effect (ADE)** – Adverse event related to the use of a tested medical device.

Note 1: this definition includes adverse events resulting from insufficient or inadequate instructions for use, deployment, implantation, installation, or operation, or any malfunction of the investigational medical device.

Note 2: this definition includes any event resulting from an error use or from intentional misuse of the investigational medical device.

#### 7.2 DEVICE DEFICIENCIES

**Device Deficiency** – Inadequacy of a medical device with respect to its identity, quality, durability, reliability, safety or performance

Note: device deficiencies include malfunctions, misuse or use errors, and inadequate labelling.

#### 7.3 SERIOUS ADVERSE EVENTS, SERIOUS ADVERSE DEVICE EFFECT AND UNANTICIPATED SERIOUS ADVERSE DEVICE EFFECTS

**Serious Adverse Event (SAE)** – Adverse event that:

a) led to death

b) led to a serious deterioration in the health of the subject that

- 1) resulted in a life-threatening illness or injury,
- 2) resulted in a permanent impairment of a body structure or a body function
- 3) required in-patient hospitalization or prolongation of existing hospitalization
- 4) resulted in medical or surgical intervention to prevent permanent impairment to body structure or a body function

**Serious Adverse Device Effect (SADE)** – Adverse device effect that has resulted in any of the consequences characteristic of a serious adverse event.

**Unanticipated Serious Adverse Device Effect (USADE)** – Serious adverse device effect which by its nature, incidence, severity or outcome has not been identified in the current version of the risk analysis report.

Note: anticipated serious adverse device effect (ASADE) is an effect which by its nature, incidence, severity or outcome has been identified in the risk analysis report.

#### 7.4 TIME PERIOD FOR PRINCIPAL INVESTIGATOR TO REPORT ADVERSE EVENTS

The PI shall:

- a) record every adverse event and observed device deficiency, together with an assessment of the event and report it to the local IRB and to 3M Oral Care as soon as possible and without undue delay;
- b) report all serious adverse events and all adverse events and device deficiencies that could have led to a serious adverse device effect to the local IRB and to 3M Oral Care within 24 hours or sooner if possible after becoming aware of the situation; this information shall be promptly followed by detailed written reports as necessary so that 3M Oral Care can evaluate the event and report to the proper regulatory authority and/or IRB;
- c) supply the local IRB and 3M Oral Care with any additional requested information related to the safety reporting of a particular event.

